### 6.1.14. Safety Analyses

The safety and tolerability of treatment with duloxetine will be assessed by summarizing the following:

- Treatment-emergent adverse events (TEAEs)

- Serious Adverse Events (SAEs)
- Vital signs
- Height
- Weight
- Rates and reasons for early discontinuation
- Laboratory measurements and electrocardiograms (ECG)
- Suicide risk and suicide-related events (behavior and/or ideation) as assessed by the Columbia-Suicide Severity Rating Scale (C-SSRS)

For Study Period II, statistical comparisons will be conducted to compare treatment groups. For Study Period III, descriptive statistics only will be presented for each treatment group.

The baseline periods for all safety data are as described for safety variables in Table HMGW.6.1 unless otherwise specified.

#### **6.1.14.1. Adverse Events**

All adverse events (AEs) will be coded using the Medical Dictionary for Regulatory Activities (MedDRA). In this thesaurus, each verbatim term is mapped to a “preferred” MedDRA term, which is then mapped to a system organ class.

An adverse event is treatment emergent if it is newly occurring or worsened in severity during post-baseline compared with baseline. The evaluations of adverse events will include separate summaries for Study Periods II, III, and IV of the number and percentage of patients with treatment-emergent adverse events (TEAEs), serious adverse events (SAEs) including deaths, and discontinuations due to AEs. Also, the TEAEs for patients who are initially randomized to duloxetine will be summarized for SP II/III. The TEAEs will be summarized by severity and MedDRA preferred term. The TEAEs will be summarized by system organ class and MedDRA preferred term. Adverse events will be summarized by MedDRA preferred term.

Any event having an onset date within the post-baseline range of its Study Period is a TEAE. For each event, the severity level of an event at first report and the change in severity level is recorded according to the patient’s or physician’s perceived severity of the event (mild, moderate, or severe). In addition, a change in severity to more severe than that recorded during the baseline period can be recorded during the study. For each event, the maximum severity during visits for baseline will be used as the baseline severity. If the maximum severity during post-baseline visits for the study period is greater than the baseline severity, the event is considered to be treatment-emergent.

For Study Period II, an adverse event is treatment emergent if the event onset date falls after visit 2 and prior to visit date of visit 8. An event which was ongoing during the baseline period becomes treatment emergent if it worsens in severity after visit 2 and prior to visit date of visit 8, compared with the maximum severity prior to visit 2. For Study Period III, unless stated otherwise, an adverse event is treatment emergent if the onset date falls after visit 8 and prior to visit date of visit 15. An event which was ongoing during the earlier study periods becomes treatment emergent if it worsens in severity after visit 8 and prior to visit date of visit 15,

compared with the maximum severity between visit 7 and 8 during Study Period II. For Study Period II, all SAEs from after visit 2 to visit 8 will be summarized. For Study Period III, all SAEs from after visit 8 to visit 15 will be summarized. For Study Period IV, all SAEs during the taper phase will be summarized.

Discontinuation emergent AEs will be summarized for patients entering Study Period IV from Study Period II and for patients entering Study Period IV from Study Period III. For these analyses, the baseline period will be the last two visits during the previous study period. Any AEs with an onset or worsening severity on or after the start of Study Period IV, compared to the maximum severity during the baseline period, will be considered discontinuation emergent for the taper phase.

Listings for AEs and pre-existing conditions, SAEs, discontinuations due to AEs or death will be presented.

The Kaplan-Meier survival curve for time to onset of the most common TEAEs during SP II/III will be calculated for patients who are initially randomized to duloxetine. In the calculation, patients who do not have the event will be considered as right-censored observation. The same Kaplan-Meier survival curve will be calculated for time to discontinuation due to adverse event.

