**Table HMGW.6.1 Patient Population with Baseline and Post-baseline Definitions by Study Period and Type of Analysis**

Study Period / Analysis	Patient Population	Baseline Definition	Post-baseline Definition
Acute Phase			
Efficacy	Patients with a baseline and at least one post-baseline observation	Last of Visits 1-2	All Visits 3-8
TEAEs	All randomized patients	All Visits 1-2	All Visits 2.01-8
SAE and DCAE	All randomized patients	NA	All Visits 2.01-8
C-SSRS categorical analyses	All randomized patients	Lifetime baseline: All Visits 1-2 Lead-in baseline: Visit 2	All Visits 2.01-8
Treatment Emergent Abnormal Labs	Patients with normal laboratory values at all nonmissing baseline visits (with respect to direction being analyzed) and who have at least one post-baseline observation	All of Visits 1-2	All Visits 2.01-8
Treatment emergent low blood pressure	Patients with normal values at all nonmissing baseline visits (with respect to direction being analyzed) and who have at least one post-baseline observation. See Table HMGW.6.4 for normal limits of blood pressure.	Minimum value from Visits 1-2	All Visits 2.01-8
PCS in vital signs, weight, sustained blood pressure analyses	Vital signs: Patients with normal values at all nonmissing baseline visits (with respect to direction being analyzed) and who have at least one post-baseline observation. See Table HMGW.6.4 for normal limits of vital signs. Weight:	Low: Minimum value from Visits 1-2 High: Maximum value from Visits 1-2	All Visits 2.01-8

	Patients with non-missing baseline and at least one post-baseline value.		
Treatment-emergent changes in ECG intervals and heart rate	Patients with normal values at all nonmissing baseline visits (with respect to direction being analyzed) and who have at least one post-baseline observation. See Table HMGW.6.8 for normal limits of ECG.	Low: Minimum value from Visits 1-2 High: Maximum value from Visits 1-2	All Visits 2.01-8
Continuous Safety measures	Patients with a baseline and at least one post-baseline observation	Last of Visits 1-2	All Visits 3-8
Extension Phase			
Efficacy	Patients with a baseline and at least one post-baseline observation	Last of Visits 3-8	All Visits 9-15
TEAEs	All randomized patients entering extension phase	Maximum severity between $7 \leq \text{Visit} \leq 8$	All Visits 8.01-15
SAE and DCAE	All randomized patients entering extension phase	NA	All Visits 8.01-15

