#### **6.1.14.4. Electrocardiograms**

In this study, 12-lead ECGs will be obtained in triplicate at defined study visits (Visits 1, 8, 12, and 15/discontinuation), with each measurement done approximately 1 minute apart.

The ECGs recordings will be electronically transmitted to a centralized ECG vendor who will complete the ECG overread. All three of the ECG recordings will be overread by the vendor. For patient management purposes during the study, the vendor will send the study site a full overread/interpretation for only one of the triplicate ECG recordings (the first readable) obtained at each visit. For data analysis purpose, the vendor overread of QT, PR, RR and QRS measurements (the non-missing values) from all 3 ECG recordings will be averaged, and these averaged values will represent the ECG results for each patient/visit. The QTc result for each ECG recording will be determined using the HR, RR and QT intervals and then the average QTc will be calculated.

The incidence of patients meeting criteria for treatment-emergent abnormal values at endpoint (LOCF) and at any time will be summarized for SP II, SP III and SP II/III, and compared between treatment groups for SP II. The abnormality criteria are presented in Table HMGW.6.7. In those analyses, only patients with normal values at all baseline visits with respect to direction being analyzed will be included. The normal limits at baseline are described in Table HMGW 6.8. The Fridericia's corrected QT interval (QTcF) (msec) will be calculated as  $QT/RR^{1/3}$ . The Bazette's corrected QT interval (QTcB) (msec) will be calculated as  $QT/RR^{1/2}$ .

In addition to categorical analyses of the QTc intervals based on absolute values, it is customary (and expected by regulatory bodies, particularly the Committee for Proprietary medicinal Products [CPMP]) that the proportion of subjects with increases from baseline above certain thresholds also be analyzed. These thresholds are based on estimates of normal variance (versus drug-induced changes) in QTc intervals. These thresholds are:

$\geq 30$  msec

$\geq 60$  msec

$\geq 75$  msec

A listing of patients with treatment-emergent abnormal values using the criteria in Table HMGW.6.7 will be presented.

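### The period-specific TEAE sentences in SAP 6.1.14.1 leave out the Visit 8 and Visit 15 dates, which Table HMGW.6.1, the section's general TEAE rule and the SAE windows include

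*SAP*

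**What the plan says.** Section 6.1.14.1 gives period-specific rules for when an adverse event is treatment emergent.

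- **Study Period II, onset:** "an adverse event is treatment emergent if the event onset date falls after visit 2 and prior to visit date of visit 8".
- **Study Period II, worsening of an ongoing event:** it counts if "it worsens in severity after visit 2 and prior to visit date of visit 8".
- **Study Period III, onset:** "an adverse event is treatment emergent if the onset date falls after visit 8 and prior to visit date of visit 15".
- **Study Period III, worsening:** it counts if "it worsens in severity after visit 8 and prior to visit date of visit 15".

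Three other statements draw the boundary differently.

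- **General rule, same section:** "Any event having an onset date within the post-baseline range of its Study Period is a TEAE".
- **Table HMGW.6.1, TEAE rows:** the acute-phase post-baseline range is "All Visits 2.01-8", and the extension-phase range is Visits 8.01 to 15. Each includes its closing visit.
- **SAE rule, same section:** "For Study Period II, all SAEs from after visit 2 to visit 8 will be summarized". The Study Period III sentence likewise runs to Visit 15. Neither stops short of the visit date.

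**The concern.** Read literally, the period-specific sentences give the Visit 8 date to no period. It is too late for Study Period II, which must end before that date, and too early for Study Period III, which begins after the visit. The Visit 15 date is outside Study Period III for the same reason. The exclusive bound appears in all four clauses, so a programmer has no cue that it is a slip.

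Two things are at stake. First, two programmers working from the same SAP could produce different TEAE tables, because it does not say whether the text or the table takes precedence. Second, the safety tables could disagree: an SAE starting on the Visit 8 date would be in the Study Period II SAE summary but missing from the Study Period II TEAE summary. Study Period II is also the period in which the safety of the two arms is compared statistically (Section 6.1.14).

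The closing visit is also a day of scheduled assessment. Section 6.1.14.4 says "12-lead ECGs will be obtained in triplicate at defined study visits (Visits 1, 8, 12, and 15/discontinuation", and Section 6.1.14.3 has vital signs taken at every visit.

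**Working it through.** No figure in the SAP needs reproducing. The check places an onset (or worsening) date at each boundary and applies each rule.

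| Date of onset or worsening | Period-specific sentences, 6.1.14.1 | Table HMGW.6.1 TEAE rows | SAE sentences, 6.1.14.1 |
|---|---|---|---|
| Day before Visit 8 | SP II | SP II | SP II |
| Visit 8 date | neither | SP II | SP II |
| Day after Visit 8 | SP III | SP III | SP III |
| Day before Visit 15 | SP III | SP III | SP III |
| Visit 15 date | not SP III | SP III | SP III |

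The general rule refers to the post-baseline range, which Table HMGW.6.1 defines, so it agrees with the table column. Section 6.1.14.1 thus disagrees with itself as well as with the table.

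**Does Study Period III recover a Visit 8 event?** No.

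- Table HMGW.6.1 starts the extension range at Visit 8.01, which its footnote defines as an unscheduled visit after Visit 8.
- The Study Period III severity baseline is the maximum between Visits 7 and 8. An event present at Visit 8 is therefore baseline for Study Period III and reappears only if it later worsens.
- Section 6.1.10 sets the first Study Period III dose one day after the Visit 8 date, so that date belongs with double-blind treatment.

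**Does the combined summary recover it?** Not clearly. Section 6.1.14.1 plans a Study Period II/III TEAE summary for patients randomized to duloxetine, but the combined part of Table HMGW.6.1 has no TEAE row.

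**Size with evenly spread onsets, at nominal period lengths.**

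- Study Period II: 13 weeks × 7 = 91 days after Visit 2, counting the Visit 8 date. The narrow sentences cover 90. Loss = 1/91 = 1.1%.
- Study Period III: 26 weeks × 7 = 182 days after Visit 8, counting the Visit 15 date. The narrow sentences cover 181. Loss = 1/182 = 0.5%.

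**ECG-detected events.** Scheduled ECGs are at Visits 1, 8, 12 and 15/discontinuation. For a patient who completes Study Period II, Visit 8 is thus the only scheduled post-baseline ECG of that period. If an adverse event first found on that ECG is given the visit date as its onset, the narrow sentence excludes it. The SAP does not say how onset dates are assigned, so this is conditional and no percentage can be attached to it.

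**The case against.** The strongest reply is that the SAP already contains an inclusive rule. The general sentence and Table HMGW.6.1 together capture events on the Visit 8 and Visit 15 dates, and the section also judges worsening by maximum severity over the post-baseline visits, of which Visit 8 is one. This stands to the extent that a loss is possible, not established: it occurs only if the narrower sentences are programmed over the general rule and the table. It does not remove the contradiction, because those sentences are the more specific ones.

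A reader might go further and infer that TEAE counts will be understated, that nearly all ECG-detected events of the acute phase will be missed, or that laboratory findings at these visits will be lost. The SAP does not support these readings.

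- The near-total ECG loss rests on an onset-dating convention that is not stated.
- The SAP does not say that laboratory tests are done at Visits 8 or 15. Table HMGW.6.2 says only that the first scheduled post-baseline laboratory visit is Visit 6.
- Vital signs are taken at every visit, so Visit 8 is one of six scheduled post-baseline visits (3 to 8) in the acute phase.
- Laboratory, vital-sign and ECG abnormalities have their own categorical analyses with post-baseline ranges that include Visits 8 and 15, and adverse events are listed. At most, the adverse event term is missing from a TEAE table.

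Two further points are fair. The rule is the same in both arms, so no direction of bias is shown. And at Visit 15, a tapering patient's event might already be summarized as discontinuation emergent, if Study Period IV starts that day. That is a separate category, and patients finishing Study Period III on 30 mg are not required to taper, so it does not close the gap. It does mean that a correction must also settle the taper boundary.

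**Conclusion.** The point holds as an internal contradiction in the definition of a core safety endpoint. The four period-specific clauses exclude the Visit 8 and Visit 15 dates. Table HMGW.6.1, the general TEAE rule and the SAE windows include them.

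The expected effect is small: about 1.1% of days in Study Period II and 0.5% in Study Period III, assuming nominal period lengths, evenly spread onsets and programming from the narrow sentences. It could be larger for adverse events first detected by the Visit 8 ECG, on the further assumption that they are dated to the visit. No efficacy result is affected. The correction is worth making because the TEAE and SAE tables could otherwise disagree for the same event, and because the choice between the two rules should not be left to the programmer.

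**What to change.** 1. In Section 6.1.14.1, change the four upper bounds (onset and worsening, Study Periods II and III) so that each window closes on or before the visit date of Visit 8 or Visit 15. This matches Table HMGW.6.1 and the SAE sentences. The Visit 8 date then falls only in Study Period II and the Visit 15 date only in Study Period III, with no gap or overlap between the two.
2. State that, for the adverse event analyses of patients entering taper, Study Period IV begins after the last Study Period II or III visit date. No event is then counted both as a TEAE and as discontinuation emergent. This fits the existing taper baseline in Table HMGW.6.1, which already includes the last visit before taper.

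The cost is a wording change in the SAP and the matching date conditions in the TEAE program. No new data are needed.

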### 5.1. Summary of Study Design

Study F1J-MC-HMGW (HMGW) is a Phase 3b, multicenter, randomized clinical trial of duloxetine versus placebo for the treatment of JPFS in adolescents. The study design includes 4 study periods. Following Study Period I (screening phase), eligible patients enter Study Period II, the acute 13-week parallel, randomized, double-blind, placebo-controlled treatment period of duloxetine 30/60 mg QD. Upon completion of the 13-week double-blind period, patients enter Study Period III, a 26-week, open-label extension phase of duloxetine 30/60 mg QD. A 1-week drug taper period (Study Period IV) is required for all patients who discontinue for any reason between Visit 4 to Visit 8 during Study Period II, or who complete/discontinue Study Period III on duloxetine 60 mg QD.

Figure HMGW.5.1 illustrates the study design.

Abbreviations: DB = double-blind; DLX = duloxetine; OL = open-label; QD = once-daily

a After Visit 3, patients increased to 60 mg duloxetine can have their dose decreased 1 time, at a scheduled or unscheduled Visit. Once 60 mg dose is decreased to 30 mg, it cannot be increased again during Study Period II.

b At Visits 4 through 8, patients randomized to placebo or DLX 30 mg who discontinue prior to entering the open-label extension treatment period (Study Period III) will receive placebo in the drug taper period.

c At Visits 9 through 14 in Study Period III, dose increases are permitted at scheduled visits (to a maximum dose of 60 mg QD) and dose decreases are permitted at scheduled or unscheduled visits (to a minimum dose of 30 mg QD).

d Patients who complete/discontinue Study Period III on DLX 30 mg do not need to enter the drug taper period.

**Figure HMGW.5.1** Illustration of study design for Protocol F1J-MC-HMGW.

Study Period I is a screening period of approximately 1 week in duration, but not more than 30 days, during which patients will be screened for study eligibility.

Study Period II is a 13-week, acute treatment period. During Study Period II, at Visit 2, patients who meet all study criteria for enrollment will be randomly assigned in a 1:1 ratio to duloxetine or placebo by a computer-generated random sequence using an interactive voice response system (IVRS). All patients will receive investigational product (IP) beginning at Visit 2 and will be instructed to start taking their IP the morning after Visit 2.

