## **5.2. Determination of Sample Size**

Approximately 184 patients will be randomized in a 1:1 ratio to the duloxetine and placebo treatment groups. This study is to assess the difference of the mean change in BPI average pain severity from baseline to the last time point (Visit 8, Week 13) in Study Period II between treatment groups. Assuming that there will be some missing post-baseline data, and about 81% completion rate at acute phase by Visit 8 or Week 13, this sample size will provide at least 80% power to detect the treatment difference of 1.0 point with  $\alpha=.05$ . All the parameters used in the sample size calculations were based on the MMRM analysis of data from 3-month, placebo-controlled, acute treatment period in 2 adult FM studies: Study F1J-MC-HMCA and Study F1J-MC-HMCJ.

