
6. Time to event variable:  a. Time to first 30% reduction in BPI average pain score  b. Time to first 50% reduction in BPI average pain score  c. Time to sustained response
	
a. For the patients with a 30% reduction at a visit in the treatment phase in SP II, time = days from the date of the visit that the earliest 30% reduction is observed to the date of the first day of SP II. The date of the first day of SP II is the randomization date.  b. For the patients with a 50% reduction at a visit in the treatment phase in SP II, time = days from the date of the visit that the earliest 50% reduction is observed to the date of the first day of SP II.  c. For the sustained responders defined above in SP II, time = the days from the date of the visit which is the earlier visit from which the sustained response is observed to the date of the first day of SP II.
	
For Variables 6.a to 6.c, the Kaplan-Meier survival curves of time to event will be calculated by treatment group for Study Period II. In the calculation, patients who do not have the event will be considered as right-censored observation. The comparison of the survival curves between treatment groups will be conducted by a log-rank test and stratified log-rank test controlling for pooled investigator.

Abbreviations: ANCOVA = analysis of covariance; BOCF = baseline observation carried forward; BPI = Brief Pain Inventory-Adolescent Version; CDI = Children's Depression Inventory; CGI-S = Clinical Global Impressions of Severity; eCRF = electronic case report form; FDI = Functional Disability Inventory; LOCF = last observation carried forward; MASC = Multidimensional Anxiety Scale for Children; PPQ = Pediatric Pain Questionnaire.

The treatment-by-investigator interaction will be tested using an ANCOVA model. When the interaction is statistically significant, the nature of the interaction will be investigated.

Descriptive statistics will be used to summarize all variables presented in HMGW.6.3 except variables 3a-b, 5(b, d, h) and 6a-c by treatment group for all ITT patients entering Study Period III. Descriptive statistics will be used to summarize variables 1a, 2a-f, and 4a-e for Study Period II/III. For continuous measures, when appropriate, within treatment testing of change from baseline will be conducted for SP III and SP II/III.

For efficacy measures, data from all visits will be listed.

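### The Kaplan-Meier curve for discontinuation due to an adverse event treats other withdrawals as ordinary censoring, so with censoring at exit it overstates the cumulative proportion, by about 3 to 4 points at 39 weeks

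*SAP*

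**What the plan says.** SAP Section 6.1.14.1 first plans Kaplan-Meier curves for onset of the most common treatment-emergent events over Study Periods II and III, which "will be calculated for patients who are initially randomized to duloxetine". It sets the censoring rule: "In the calculation, patients who do not have the event will be considered as right-censored observation". It then extends the method: "The same Kaplan-Meier survival curve will be calculated for time to discontinuation due to adverse event". It names no competing event and no censoring date.

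The same rule appears in Table HMGW.6.3 for variables 6a to 6c (time to first 30% reduction, first 50% reduction and sustained response in BPI average pain). There "the Kaplan-Meier survival curves of time to event will be calculated by treatment group for Study Period II", and the arms are compared in a test "conducted by a log-rank test and stratified log-rank test controlling for pooled investigator". Time is defined only for patients who have the event.

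Variable 5g in the same table is the sustained response rate. It requires at least a 30% reduction at endpoint, reached at an earlier visit too, with at least 20% kept at any visit in between. It is restricted to patients with a baseline and at least two post-baseline values. Variable 6c takes its events from that definition.

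**The concern.** Reasons for discontinuation exclude one another. A patient who leaves for lack of efficacy or by own decision will never be a discontinuation due to an adverse event. Kaplan-Meier with censoring at exit removes that patient from the risk set and in effect assigns the future event rate of those who stay. One minus Kaplan-Meier then estimates the proportion who would stop for an adverse event if nobody could leave for any other reason. It does not estimate the proportion who do stop for one.

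The figure matters because no combined table stands beside it. Section 6.1.14.1 counts discontinuations due to adverse events separately for Study Periods II, III and IV. Its combined Study Period II/III summary covers treatment-emergent events only, and the combined block of Table HMGW.6.1 has no row for adverse events leading to discontinuation. The by-period percentages also change denominator, from all randomized patients to those entering the extension. The curve is therefore the only planned cumulative display over 39 weeks.

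Variable 6c has a related problem. A patient who withdraws without meeting the definition at the last observation has a known outcome and, with at least two post-baseline values, counts as a non-responder in 5g. Censored at exit in 6c, the same patient is treated as if the outcome were still open.

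**Working it through.** The SAP states no figure for these curves, so there is none to reproduce.

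**Inputs from the SAP**
- Dropout in Study Period II: Section 5.2 assumes "about 81% completion rate at acute phase by Visit 8 or Week 13", so 19% leave by Week 13.
- Follow-up: 13 weeks, after which "patients enter Study Period III, a 26-week, open-label extension phase of duloxetine 30/60 mg QD" (Section 5.1), so 13 + 26 = 39 weeks.
- Duloxetine arm: 184 randomized 1:1 (Section 5.2), so 92.

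**Assumptions, not in the SAP**
- Constant hazards, with the 13-week dropout rate continuing to Week 39.
- Adverse events account for a share s of dropouts, with s = 25%, 50% or 75%.
- Patients who leave for another reason are censored at exit.

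**Formulas**, with T in units of 13 weeks:
- Total dropout hazard: H = −ln(0.81) = 0.2107.
- One minus Kaplan-Meier: 1 − exp(−s·H·T).
- Cumulative incidence: s·(1 − exp(−H·T)) = s·(1 − 0.81^T).

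Total dropout is 19.0% at 13 weeks and 1 − 0.81³ = 46.9% at 39 weeks. For s = 50% at 39 weeks, one minus Kaplan-Meier is 1 − exp(−0.5 × 0.2107 × 3) = 27.1%, and cumulative incidence is 0.5 × 46.9% = 23.4%.

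| Week | Share s | 1 − Kaplan-Meier | Cumulative incidence | Excess (points) |
|---|---|---|---|---|
| 13 | 25% | 5.1% | 4.8% | 0.4 |
| 13 | 50% | 10.0% | 9.5% | 0.5 |
| 13 | 75% | 14.6% | 14.3% | 0.4 |
| 39 | 25% | 14.6% | 11.7% | 2.9 |
| 39 | 50% | 27.1% | 23.4% | 3.7 |
| 39 | 75% | 37.8% | 35.1% | 2.6 |

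Excesses are taken before rounding. At 39 weeks the relative overstatement is 7% to 25% (ratios 1.074 to 1.248).

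**Simulation.** In 2,000 simulated arms of 92 at s = 50%, the means at 39 weeks were 27.1% for one minus Kaplan-Meier and 23.4% for the proportion who stopped for an adverse event. The first was never below the second. With patients without the event censored at period end instead, Kaplan-Meier also gave 23.4% and the excess vanished. The unstated censoring date thus decides whether there is any excess.

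**6c against 5g.** Take a patient with several post-baseline values who withdraws with less than a 30% reduction at the last one. In 5g that patient is in the denominator and not in the numerator. In 6c with censoring at exit, the patient leaves the risk set and the curve continues on those who remain, so it can end above the 5g rate. If the patient is kept as a competing event and nobody is censored before period end, cumulative incidence at the end of Study Period II equals sustained responders over all patients analysed. That is the 5g rate, provided both use the same analysis set.

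**The case against.** The strongest defence has five parts.

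- **The curve is descriptive.** It covers one group and carries no test, and the SAP never says that one minus Kaplan-Meier will be reported as the proportion who stop. This stands. It limits the consequence but does not change what readers take from such a curve.
- **The crude figures exist.** Section 6.1.7 tabulates disposition by period and by visit, with reasons. A reader could add the duloxetine counts from the two periods over those randomized. This partly stands, but the plan does not present that sum, and it would disagree with the plotted curve.
- **The censoring date is unstated.** Under period-end censoring there is no overstatement. This stands, so the point is conditional on censoring at exit, which is the ordinary reading. It also shows why the date must be written down.
- **For 6a and 6b, censoring is defensible.** A reader might infer that these curves also overstate response. The documents do not support that as a flat statement. Time to first response can target response had patients stayed, and non-informative censoring is in the spirit of the missing-at-random repeated measures analysis in Section 6.1.4.
- **Counting dropouts as no change elsewhere is no contradiction.** A reader might see a conflict with the baseline-carried-forward analyses and variable 5h. Section 6.1.4 deliberately plans several missing-data approaches, and the table also has last-observation and repeated-measures response analyses. First response in 6a and 6b would also differ from response at endpoint in 5a to 5d under any estimator.

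The last two parts do not rescue 6c, which uses the event definition of 5g.

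**Conclusion.** The point holds for time to discontinuation due to an adverse event, given censoring at exit. The size rests on constant hazards, continuation of the assumed 13-week dropout rate and the assumed adverse-event shares. Only the 81% completion rate and the 13 and 26 weeks come from the SAP.

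It holds for 6c as an inconsistency with 5g, again if withdrawn patients are censored at exit. The SAP gives no sustained response rate from which to size it.

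Three stronger readings should be resisted:
- **Arms not comparable.** A reader might infer that the adverse-event curves of the two arms cannot be compared. Only duloxetine is plotted.
- **A larger excess.** If 20% stopped for an adverse event and 40% for other reasons, the curve would show 26.3%, an excess of 6.3 points. That needs 60% total dropout, against the 46.9% that follows from the SAP's own rate.
- **Invalid tests.** The log-rank tests for 6a to 6c remain valid as cause-specific comparisons.

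This is a minor improvement. Neither the primary analysis nor the futility rule is touched.

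**What to change.** 1. **Discontinuation due to an adverse event (Section 6.1.14.1).** Replace the Kaplan-Meier curve with Aalen-Johansen cumulative incidence over Study Periods II and III. Treat discontinuation for any other reason as the competing event, and censor only at the end of the period or at sponsor termination of the trial.
2. **Variable 6c (Table HMGW.6.3).** Keep a withdrawn patient who does not meet the definition at the last observation as a non-responder, by way of a competing event. Use the 5g analysis set, so that the final value agrees with 5g.
3. **Variables 6a and 6b.** Kaplan-Meier may stay. State the censoring date and that censoring is assumed non-informative.
4. **Tests.** Keep the log-rank tests. Gray's test is not needed, and it would add comparisons to a plan that makes no multiplicity adjustment.

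The cost is a few lines of SAP text and a standard procedure. Discontinuation reasons are already tabulated under Section 6.1.7, and disposition dates are already used in Section 6.1.10. The 6c curve may look slightly less favourable.
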